3.5. Adjustments for Covariates

No formal statistical analyses that adjust for possible covariate effects are planned.

3.6. Multiple Comparisons/Multiplicity

Multiplicity is not of concern for this study with a descriptive interpretation.

3.7. Subpopulations

Patients who have pre-existing cardiac amyloid involvement will be eligible for inclusion in the cardiac subgroup for analysis. The inclusion criteria are the following:

- 1) Have a left ventricular wall thickness of ≥ 13 mm on transthoracic echocardiogram;
- 2) Be normotensive or have hypertension that is well-controlled;
- 3) No aortic valve disease.

Patients enrolled in the cardiac subgroup will complete additional clinical activity assessments to evaluate cardiac structure/function. This will be achieved through echocardiograms and monitoring of NT-proBNP and troponin I.

Patients will be eligible for inclusion in the PK/PD subgroup if their last dose of patisiran was administered at least 6 months prior to the first dose in this study. Patients enrolled in the PK/PD subgroup will have additional samples taken for evaluation of PK and PD (TTR and secondary PD biomarkers [RBP and vitamin A]).

3.8. Withdrawals, Dropouts, Loss to Follow-up

Patients are free to withdraw from the study at any time and for any reason, without penalty to their continuing medical care. A patient will be considered to have completed the study if the patient completes Year 2 efficacy assessments and either the 21-day or the 56-day follow-up visit. Every effort should be made to also complete the Early Termination (ET) visit, if applicable.

In the event a patient withdraws early from the study, the contract research organization (CRO) Medical Monitor must be informed immediately. If there is a medical reason for withdrawal, the patient will remain under the supervision of the Investigator for protocol-specified safety follow up procedures.

Patients who voluntarily withdraw are termed dropouts. Dropouts will not be replaced.

If a patient is withdrawn/withdraws every effort should be made to conduct the ET visit. Patients who fail to return for final evaluations will be contacted by the site in an attempt to have them comply with the protocol. The site will follow up by telephone at least twice and send a registered letter to any patient who fails to return for the final evaluation.

When a patient withdraws from the study, the primary reason for discontinuation must be recorded in the appropriate section of the electronic case report form (eCRF) and all efforts will be made to complete and report the observations as thoroughly as possible.

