4.5 Early Patient Withdrawal

Patients are free to withdraw from the study at any time and for any reason, without penalty to their continuing medical care. A patient will be considered to have completed the study if the patient completes protocol-specified procedures up through the 21-day Follow-up visit for patients continuing into the global extension study, and up through the 56-day Follow-up visit for Year 2 for patients not continuing into the global extension study. For patients who withdraw from the study early, every effort should be made to complete the Early Termination (ET) visit.

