6 STUDY VISITS

The duration of a patient's participation in this study is approximately 2 years and 4 months.

Screening/Baseline evaluations are to be performed within 28 days before receiving the first dose of study drug, as indicated in Table 1-1 and (Appendix 2 provides the schedule of assessments for patients administered ALN-TTR02 once every 4 weeks). Patients determined to be eligible based on Screening/Baseline assessments will receive treatment (IV infusion of study drug) once every 3 or 4 weeks; based on results from the ongoing ALN-TTR02-002 study where the safety and PD of 2 dosing schedules are being evaluated. Patients will remain at the study site for at least 1 hour following completion of dosing for observation and for PK sampling. Subjects in the PK/PD subgroup will remain at the study site for 6 hours following completion of dosing following the first dose and the doses given at 8 and 24 months for additional PK sampling. Patients will return to the study site for clinical activity assessments approximately once every 6 months.

All patients who discontinue the study before the 56-day Follow-up visit (or before the 21-day Follow-up visit for those patients continuing into the global extension study) will return to the study site for their Early Termination visit assessments.

Visiting nurses may conduct interim PK/PD visits.

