6.2.5 Follow-Up Visits

Patients will return to the study site for 2 follow-up visits (approximately 21 and 56 days after receiving their last dose of ALN-TTR02). If a patient enrolls in the global extension study, the patient will not have to complete the 56-day follow-up assessments. Patients who do not enroll in the extension study will need to complete both follow-up visits.

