		55 & 82	58 & 85	61 & 88	64 & 91	67 & 94	70 & 97	73 & 100	76 & 103	79 & 106	81 & 108			
	Study Day	D378 & D567	D399 & D588	D420 & D609	D441 & D630	D462 & D651	D483 & D672	D504 & D693	D525 & D714	D546 & D735	D560 & D749	D756	D791	N/A
	Window	±3D	±5D	±5D	±5D	2D to 7D								
VDT ^k											X			X ⁱ
HRdb ^k											X			X ⁱ
Grip Strength ^{k,l}											X			X ⁱ
10-Meter Walk Test ^{k,m}											X			X ⁱ
NIS ^k											X			X ⁱ
Skin Punch Biopsy (IENFD & SGFND) ^a											X			X ⁱ
mBMI											X			X ⁱ
FAP Stage and PND Score											X			X ⁱ
COMPASS 31											X			X ⁱ
QOL and Disability Questionnaires ^o											X			X ⁱ
Premedication Administration ^p	X	X	X	X	X	X	X	X	X					
Study Drug Administration ^q	X	X	X	X	X	X	X	X	X					
Plasma PK Sampling ^r					X					X	X	X	X	X
Urine PK Sampling ^s					X					X	X			X

Procedure	Visit Type	Dosing										Mid-year/ Annual Efficacy Assess- ment	21- and 56-day Follow-up ^a		Early Termination
		55 & 82	58 & 85	61 & 88	64 & 91	67 & 94	70 & 97	73 & 100	76 & 103	79 & 106	81 & 108		109	114	
	Study Day	D378 & D567	D399 & D588	D420 & D609	D441 & D630	D462 & D651	D483 & D672	D504 & D693	D525 & D714	D546 & D735	D560 & D749	D756	D791	N/A	
	Window	±3D	±3D	±3D	±5D	±5D	±5D	2D to 7D							
PK/PD Subgroup Only:															
TTR (ELISA and turbidimetric)											X ^t				
RBP and Vitamin A											X ^t				
Plasma PK Sampling											X ^u				
Urine PK Sampling											X ^v				
Cardiac Subgroup Only:															
Echocardiogram												X			X
Troponin I and NT-proBNP						X					X				X
Concomitant Medications								X ^w							
Adverse Events								X ^x							

Note: The schedule of assessments for patients administered ALN-TTR02 once every 4 weeks is provided in Appendix 2.

- a If a patient enrolls in the global extension study, the patient will only have to complete the 21-day follow-up assessments (Day 756) and not the 56-day follow-up assessments (Day 791). Patients who do not enroll in the extension study will need to complete both Follow-up visits (Days 756 and 791).
- b On dosing days, weight will be measured predose.
- c On dosing days, vital signs will be measured predose. Vital signs to include: blood pressure, pulse rate, oral body temperature, and respiratory rate. Parameters are to be measured in the supine position using an automated instrument after the patient has rested comfortably for 10 minutes.
- d Triplicate recordings will be obtained.

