4. STUDY ANALYSES

4.1. Subject Disposition

Subject disposition will be tabulated and include the number enrolled, the number dosed with patisiran, the number who completed the study, the number in each subject population for analysis, the number who withdrew prior to completing the study and reason(s) for withdrawal.

A by-subject data listing of study completion information including the reason for premature study withdrawal will be presented.

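### SAP 3.8 omits the rollover condition from the completer definition, so the disposition table can overstate completion and understate withdrawals relative to Protocol 4.5

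*SAP*

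**What the plan says.** Protocol 4.5 defines completion in two branches. A patient going on to the global extension study has completed if he or she "completes protocol-specified procedures up through the 21-day Follow-up visit for patients continuing into the global extension study". For the rest, the requirement runs "up through the 56-day Follow-up visit for Year 2 for patients not continuing into the global extension study". Other parts of the protocol agree with this. Section 6.2.5 says: "Patients who do not enroll in the extension study will need to complete both follow-up visits". Section 6 sends to an Early Termination visit "All patients who discontinue the study before the 56-day Follow-up visit", with the 21-day visit as the cut-off for patients who roll over.

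SAP 3.8 has one branch. A patient is a completer if he or she "completes Year 2 efficacy assessments and either the 21-day or the 56-day follow-up visit", and rollover is not mentioned. Yet note a to Table 1-2, reproduced in SAP 1.2.4, still requires both Day 756 and Day 791 of patients who do not enter the extension.

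SAP 4.1 builds the disposition table on this definition. It tabulates "the number who completed the study" and "the number who withdrew prior to completing the study and reason(s) for withdrawal".

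SAP Section 5, where changes from the planned analyses belong, lists no change to the completer definition. Text may be missing there, and the point does not depend on it.

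**The concern.** The two documents can give different answers for the same patient. Take someone who does not roll over, has the Year 2 efficacy assessments and the 21-day visit, and then leaves before the 56-day visit. Under the protocol this patient has discontinued early and is due an Early Termination visit, and both documents ask for a reason for withdrawal on the case report form. Under SAP 3.8 the same patient has completed, so SAP 4.1 would place the patient in the completed row, and the recorded reason would have no place in the withdrawal rows.

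What is at stake is the accuracy of one standard table in the study report, in a study whose primary objective is long-term safety. A programmer following SAP 3.8 literally would produce counts that a reader applying the protocol definition could not reproduce.

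**Working it through.** **Inputs.** All are from the once-every-3-weeks schedule in Table 1-2 (same days in both documents, with the first dose as Day 0) and from SAP 3.1.

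- Last scheduled dose: Day 735. Last efficacy visit: Day 749. Follow-up visits: Days 756 and 791.
- Planned enrolment: up to 28, not based on a power calculation.
- Number of non-rollover patients, and number who attend only one follow-up visit: not given.

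Neither document states a completion or withdrawal rate, so there is no planned figure to reproduce.

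**Step 1: the interval in dispute.** 735 + 21 = 756 and 735 + 56 = 791. The rules part over 791 − 756 = 35 days, all after the last dose and the last efficacy visit.

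**Step 2: the two rules.** Let E = Year 2 efficacy assessments done, V21 and V56 = follow-up visits attended, R = patient rolls over.

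- Protocol: E and V21 and (R or V56). This reads completing procedures up through a visit as including the earlier visits, in line with Protocol 6.2.5.
- SAP 3.8: E and (V21 or V56).

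**Step 3: compare all 2 × 2 × 2 × 2 = 16 combinations.** The rules agree on 13 and differ on 3:

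| Rolls over | Year 2 efficacy | 21-day visit | 56-day visit | Protocol 4.5 | SAP 3.8 |
|---|---|---|---|---|---|
| No | Done | Attended | Missed | Not completed | Completed |
| No | Done | Missed | Attended | Not completed | Completed |
| Yes | Done | Missed | Attended | Not completed | Completed |

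The first row is the practical case. In the second row the patient has missed a visit but not left the study, so the completed count is affected and the withdrawal count need not be. The third row is unlikely, because the 56-day visit is not required after rollover.

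**Step 4: direction.** Anyone who meets the protocol rule has E and V21, and so meets the SAP rule. The SAP completer count is therefore at least as large as the protocol count. If the protocol is read more loosely, asking only V56 of non-rollover patients, the second row drops out and the direction is the same.

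**Step 5: size.** With k discordant patients among N = 28, the completion rate shifts by 100 × k/28 percentage points. The range of k is an assumption.

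| k | Shift |
|---|---|
| 0 | 0 |
| 1 | 1/28 = 3.6 |
| 2 | 2/28 = 7.1 |
| 3 | 3/28 = 10.7 |

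**Step 6: what else uses completer status.** The three analysis sets in SAP 2.1 rest on enrolment, dosing and available PK data. None depends on completion.

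**The case against.** The best defence is that SAP 3.8 means whichever visit applies to the patient. Notes w and x to Table 1-2 name the 21-day or 56-day visit in the same way and add that the choice depends on rollover, and note a is explicit. The authors may well have intended the protocol rule. That is a fair account of intent, but SAP 3.8 does not say it, and SAP 3.8 is the sentence that defines a completer.

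The other objections limit the consequences, and they stand:

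- A reader might infer that the table does understate withdrawals, or will contradict the case report form. The documents support only that it can. If all patients roll over, or all others attend both visits, the two definitions give identical tables. The completion form is not in the documents.
- A reader might infer that an adverse event behind a departure would be lost. SAP 4.6.2 separately tabulates and lists AEs leading to discontinuation, whatever the completer status. The patient concerned has also already passed the last scheduled dose.
- A reader might infer that late follow-up is made to look complete. Protocol 6.2.5.2 lists only PD and PK sampling at the 56-day visit, and by-visit summaries report the number of subjects. AE collection for non-rollover patients does run to that visit. SAP 4.6.2's general treatment-emergent window closes at 28 days (Day 763), so a patient who leaves after Day 756 is unobserved for its last 7 days. That gap comes from the departure and is the same under either label.
- A reader might infer that only patients stopping the drug can be misclassified. One of the three discordant patterns, though improbable, is a rollover patient.

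**Conclusion.** The inconsistency is real and should be corrected. SAP 3.8 is looser than Protocol 4.5 and than the schedule note in the SAP itself. Applied as written, it can only turn protocol non-completers into completers. The consequence is confined to the disposition table: 3.6 percentage points on the completion rate per affected patient at N = 28, with an equal and opposite shift in withdrawals where the patient has actually left the study. With fewer than 28 enrolled, each such patient counts for more.

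This rests on a literal reading of SAP 3.8 and on at least one discordant patient occurring, which the documents neither state nor exclude. No efficacy, PD or AE estimate changes. The case for acting is that the rule should give one answer per patient and the correction costs almost nothing, not that a material bias has been shown.

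**What to change.** Rewrite the completer sentence in SAP 3.8 to follow Protocol 4.5: Year 2 efficacy assessments done, plus the 21-day visit for a patient entering the global extension study, or follow-up through the 56-day visit for any other patient. The same sentence should say how a non-rollover patient who misses the 21-day visit but attends the 56-day visit is counted. If the looser definition is intended, state it in SAP Section 5 as a departure from the protocol and give the reason.

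The cost is one sentence and one derivation rule in the disposition program. No data collection, analysis set or clinical procedure changes, though the reported completion rate may fall slightly. Splitting the disposition table by rollover status would make follow-up easier to read, but it is optional and not needed to remove the conflict.

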3.9. Missing, Unused, and Spurious Data

Specific algorithms will be used impute values and/or subcomponents of particular clinical activity assessments when subcomponents are missing (mNIS+7, NIS+7, EQ-5D, R-ODS, and

COMPASS; see Sections 7.1-7.4). In general, there will be no imputation for missing data for other endpoints unless specified otherwise. All data recorded on the CRF will be included in data listings that will accompany the CSR.

3.10. Visit Windows

It is expected that all visits should occur according to the protocol schedule. All data will be tabulated and analyzed per the evaluation visit as recorded on the electronic case report form (eCRF) even if the assessment is outside of the visit window. In data listings, the relative day of all dates will be presented.

Data collected at unscheduled visits will be included in by-subject data listings and figures, but no assignment to a study visit will be made for the purpose of by-visit summary tabulations. However, unscheduled visits will be considered for baseline values, as discussed in Section 3.4, and for inclusion in any categorical shift summaries (e.g., shift from baseline to “worst” post-baseline value). In addition, summaries of PD parameters (serum TTR, vitamin A, and RBP) will include separate tables and figures using All Data and Scheduled Visits Only.

Note that in the protocol Schedule of Assessments, the first dose day is designated as Day 0. In the SAP, the first dose day will be defined as Day 1 as specified in Section 3.2. In all tables, figures, and listings, on-treatment study days will equal to reported visit days + 1.

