- e On dosing days, to be performed before administration of premedications and dosing with ALN-TTR02.
- f Blood samples for TTR, RBP, and vitamin A will be collected on Day 0 at 2 separate time points: 1) prior to administration of premedications and 2) after administration of premedications but before dosing with ALN-TTR02. At all other dosing visits, a blood sample will be collected only once; prior to administration of premedications. At the

Mid-year and Annual visits, one sample should be collected on each day. Additionally, aliquots of serum samples will be taken and frozen, to permit testing of additional proteins related to FAP.

- g Blood samples for exploratory biomarkers will be collected prior to dosing with ALN-TTR02.
- h Blood samples for ADA will be collected only at the Day 735 visit (approximately 24 months), prior to dosing with ALN-TTR02.
- i To be performed only in patients who have received at least 4 doses of study drug and who withdraw >3 months after the last clinical activity assessments were performed. These tests will not be repeated.
- j The mNIS + 7 consists of the modified NIS tool (or aspects of the tool; weakness and reflexes only), NCS, QST by body surface area including TP and HP, and postural blood pressure. Every effort will be made to use the same devices for a patient throughout the duration of the study.
- k Two independent assessments will be performed at Screening/Baseline and at the Mid-year and Annual visits. The second (repeat) assessment must be conducted at least 24 hours (approximately) after the first assessment, but not more than 7 days apart.
- l Hand grip strength will be measured using a dynamometer held in the dominant hand. Every effort will be made to use the same device for a patient throughout the duration of the study. At each time point, 2 independent assessments (each assessment performed in triplicate) will be performed.
- m Patient will walk without assistance for 10 meters in order to complete the 10-meter walk test. The time required for the patient to complete 2, 8, and 10 meters will be recorded.
- n Two 3-mm skin punch biopsies are to be obtained. One will be obtained from the distal lower leg, when a patient's clinical status allows, and one from the distal thigh.
- o Quality of life and disability assessments will include the EQ5D and R-ODS questionnaires.

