1.6.1 Potential Benefit

Patisiran is a novel investigational agent intended for the treatment of FAP, a serious and life-threatening orphan disease. The therapeutic hypothesis that systemic amyloidoses can be managed by reduction in circulating levels of amyloidogenic protein has been validated in other acquired (e.g., immunoglobulin light chain systemic [AL], or amyloid A [AA]) and hereditary (e.g. Fibrinogen A α -chain, ApoA1) amyloidosis. The experience from these systemic amyloidotic disorders,^{41,42,43,44} as well as the liver transplant data in FAP, suggest that lowering of the circulating amyloidogenic protein by at least 50% is required to impact the clinical course of the disease, with reductions in protein beyond 50% providing further incremental improvements in outcomes. It is therefore postulated that the >80% suppression in *both* WT and mutant TTR observed upon administration of 0.3 mg/kg patisiran once every 21 days will result in clinical benefit in FAP patients with mild to moderate polyneuropathy. This hypothesis is further supported by evidence from tafamidis suggesting that reduction in free TTR monomer can slow neuropathy progression in early-stage V30M patients with FAP.⁴⁵

Data as of March 13, 2015 demonstrate a sustained mean serum TTR knockdown of approximately 80%, with mean nadir up to 88% between doses, for approximately 16 months. Neuropathy impairment scores were stable through 12 months with mean change in mNIS+7 and NIS of -2.5 and +0.4 points, respectively.

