6.3 Early Termination

For patients who withdraw early from the study, every effort will be made to have them return to the study site to have the following procedures performed.

- Perform a physical examination, including weight.
- Measure vital signs.
- Perform a 12-lead ECG.
- Collect blood samples for clinical laboratory tests, including:
 - Hematology
 - Serum chemistries
 - Coagulation studies
 - Thyroid function tests
- Collect blood samples for serum TTR protein and secondary PD biomarker analysis. Additionally, aliquots of serum samples will be taken and frozen, to permit testing of additional proteins related to FAP.
- Collect blood sample for PK analyses
- Collect urine sample for PK analyses
- Collect urine sample for urinalysis.
- Perform clinical activity assessments once, only in patients who withdraw >3 months after the last clinical activity assessments were performed and who received at least 4 doses of study drug.
 - mNIS + 7
 - VDT
 - Grip strength
 - Ten-meter walk test
 - mBMI
 - NIS
 - HRdb
 - COMPASS 31 survey
 - Pharmacoeconomics questionnaire
 - EQ5D
 - R-ODS
 - PND score
 - FAP stage
 - Collect paired 3-mm skin punch biopsies for IENFD analysis
- Perform an ophthalmology examination.
- For patients enrolled in the Cardiac subgroup:
 - Perform an echocardiogram

- Collect blood sample for assessment of NT-proBNP and troponin I
- Obtain concomitant medications information.
- Document any AEs.

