- e On dosing days, to be performed before dosing with ALN-TTR02.
- f Blood samples for TTR, RBP, and vitamin A will be collected on Day 0 at 2 separate time points: 1) prior to administration of premedications and 2) after administration of premedications but before dosing with ALN-TTR02. At all other dosing visits, a blood sample will be collected only once; prior to administration of premedications. At the Mid-year and Annual visits, one sample should be collected on each day. Additionally, aliquots of serum samples will be taken and frozen, to permit testing of additional proteins related to FAP.
- g Blood samples for exploratory biomarkers will be collected prior to dosing with ALN-TTR02.
- h Blood samples for ADA will be collected only at the Day 735 visit (approximately 24 months), prior to dosing with ALN-TTR02.
- i To be performed only in patients who have received at least 4 doses of study drug and who withdraw >3 months after the last clinical activity assessments were performed. These tests will not be repeated.
- j The mNIS + 7 consists of the modified NIS tool (or aspects of the tool; weakness and reflexes only), NCS, QST by body surface area including TP and HP, and postural blood pressure. Every effort will be made to use the same devices for a patient throughout the duration of the study.
- k Two independent assessments will be performed at Screening/Baseline and at the Mid-year and Annual visits. The second (repeat) assessment must be conducted at least 24 hours (approximately) after the first assessment, but not more than 7 days apart.
- l Hand grip strength will be measured using a dynamometer held in the dominant hand. Every effort will be made to use the same device for a patient throughout the duration of the study. At each time point, 2 independent assessments (each assessment performed in triplicate) will be performed.
- m Patient will walk without assistance for 10 meters in order to complete the 10-meter walk test. The time required for the patient to complete 2, 8, and 10 meters will be recorded.
- n Two 3-mm skin punch biopsies are to be obtained. One will be obtained from the distal lower leg, when a patient's clinical status allows, and one from the distal thigh.
- o Quality of life and disability assessments will include the EQ5D and R-ODS questionnaires.

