3.11. Interim Analyses

There is no formal interim analysis planned for this study. Interim data examinations may be performed, but these will be of a descriptive nature and will not involve any formal hypothesis testing. In particular, summaries of changes from baseline for clinical activity parameters will be conducted on the 6, 12, 18, and 24 month data.

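### Early Termination clinical-activity values enter none of the month 6, 12, 18 or 24 mNIS+7 change summaries, so those summaries are observed-case means

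*SAP*

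**What the plan says.** **Collection.** Protocol 6.3 lists the full battery at ET: "Perform clinical activity assessments once, only in patients who withdraw >3 months after the last clinical activity assessments were performed", with at least 4 doses also required. Footnote i to the Year 2 schedule, in the protocol and the SAP, repeats the conditions and adds "These tests will not be repeated". An ET value is therefore a single assessment, whereas scheduled visits have two. ET has its own column in the schedule.

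**Tabulation.** SAP 3.10: "All data will be tabulated and analyzed per the evaluation visit as recorded on the electronic case report form (eCRF". This applies even when the assessment is outside its window. For unscheduled visits the same section says that "no assignment to a study visit will be made for the purpose of by-visit summary tabulations"; ET is not named there.

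**Time points.** SAP 1.2.5.2 places clinical-activity assessments at baseline and months 6, 12, 18 and 24. SAP 3.11 says that "summaries of changes from baseline for clinical activity parameters will be conducted on the 6, 12, 18, and 24 month data". SAP 4.4.1 uses the same four points for the correlation of TTR reduction with mNIS+7 change. SAP 4.4 promises observed values and changes from baseline on the Full Analysis Set, and mentions neither ET nor a last value.

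**Missing data.** SAP 3.9 describes algorithms for missing subcomponents of mNIS+7 and four other instruments, then adds: "In general, there will be no imputation for missing data for other endpoints unless specified otherwise".

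**Interim reading.** Protocol 1.6.1: "Neuropathy impairment scores were stable through 12 months with mean change in mNIS+7 and NIS of -2.5 and +0.4 points, respectively".

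**The concern.** Change in mNIS+7 is a secondary objective, and in a single-arm study the by-visit mean carries the message. The analysis set is everyone enrolled, but a visit mean can use only patients assessed at that visit. If patients who leave are those whose neuropathy is progressing, the means at later visits would look more stable than the enrolled group was. For some of these patients a later mNIS+7 value will already have been collected, and the plan gives it no place in the change summaries.

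Other data types are treated differently. SAP 3.10 plans PD tables both on all data and on scheduled visits only. Protocol 9.2.3 summarises laboratory, vital-sign and ECG change to the last evaluation on study as well as by visit. Clinical activity has no counterpart to either.

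**Working it through.** There is no planned figure to reproduce. SAP 3.1 sets N at up to 28 from parent-study enrolment, without a power calculation or dropout allowance. The checks below trace the rule and then give a scale.

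**1. Where an ET value goes.** It is recorded under the ET visit, SAP 3.10 tabulates by recorded visit, and the change summaries are for months 6, 12, 18 and 24. It therefore enters none of the four. A separate ET row could be printed, but it would pool patients from different times and leave the four means as they are.

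**2. How often an ET battery is triggered.** Inputs from the every-3-week schedule: assessments at days 182, 371, 560 and 749; 3 months = 3 × 30.44 = 91.3 days; fourth dose at day 63, so the dose condition does not bind. Withdrawal is assumed uniform over 749 days.
- First interval, baseline on Day 0: 182 - 91.3 = 90.7 qualifying days.
- Each later interval: 189 - 91.3 = 97.7 days; three of them give about 293.
- Share: (90.7 + 293)/749 = 51%. With baseline 14 days before Day 0, (104.7 + 293)/749 = 53%.

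**3. Shift in one visit's mean.** With k leavers added at an average ET change d, and -2.5 assumed as the mean in the other 28 - k:

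mean = [(28 - k)(-2.5) + k·d]/28

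| k | d = +5 | d = +10 | d = +20 | d needed for a mean of 0 |
|---|---|---|---|---|
| 1 | -2.23 | -2.05 | -1.70 | +67.5 |
| 3 | -1.70 | -1.16 | -0.09 | +20.8 |
| 4 | -1.43 | -0.71 | +0.71 | +15.0 |

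For example, k = 1 and d = +5 give (27 × -2.5 + 5)/28 = -62.5/28 = -2.23. The values of k and d are assumptions. The protocol does not say how many patients lie behind -2.5.

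**4. Which row applies to a visit.** If an ET value is placed at the next scheduled time point, k leavers share one mean only if all k withdrew in the same qualifying window. Under uniform withdrawal that window is 97.7/749 = 13% of follow-up. Three leavers would contribute about 3 × 0.13 = 0.4 ET values to a given later visit, and the chance that all three fall there is 0.13³, about 0.2%. The k = 1 row is the realistic scale for a single visit.

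**5. How early an ET value can be.** It can precede the next scheduled assessment by up to 189 - 91.3, about 98 days (about 105 in the first interval if baseline was on Day -14). The midpoint between scheduled visits is 94.5 days, so an ET assessment at 92 to 94 days is slightly nearer the previous visit.

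**The case against.** The SAP nowhere says that ET values are discarded. All data are to be tabulated by recorded visit and all CRF data listed, so ET values will appear somewhere. The rule on unscheduled visits does not clearly reach ET, which is a visit type in the schedule. This stands: the exclusion from the monthly means is implied by the rules, not stated. A reader who infers that the plan throws the data away goes too far.

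A reader might also take the general statement in SAP 3.9 as proof that nothing is imputed for mNIS+7. That sentence concerns other endpoints; mNIS+7 is among the instruments carved out just before it. The mNIS+7 missing-data steps in SAP 7.1 cannot be read in the public copy. SAP 3.9 ties them to missing subcomponents, so a rule for a missed visit is unlikely there but cannot be ruled out.

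The direction of any bias is not documented. Protocol 4.5.1 lists reasons that may track worsening (a serious or intolerable adverse event, developing an exclusion condition) beside others that need not (pregnancy, protocol violation, non-compliance).

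Finally, this is a descriptive extension study whose primary objective is safety. Observed-case summaries suit that purpose, and attrition is partly visible already through the number of subjects in each summary (SAP 3.2) and the disposition table (SAP 4.1). That is a fair reason to leave the primary tables alone. It does not explain why collected values should have no place beside them.

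**Conclusion.** The point holds in a limited form. Under SAP 3.10, ET clinical-activity values enter none of the month 6, 12, 18 or 24 mNIS+7 change summaries. These are observed-case means, where a patient counts at every visit actually attended, and they may favour stability if leavers are worsening.

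On the assumptions in the working, one leaver in a visit's mean moves -2.5 to between about -2.2 (at +5) and -1.7 (at +20). A reader might infer from the table that three or four dropouts would erase the interim -2.5. The documents do not support that for a visit mean: it needs several leavers in the same interval, large ET changes, and an ET battery for each, while only 51 to 53% of possible withdrawal times trigger one. Nor do the documents show that the mNIS+7 means are in fact biased towards stability.

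With no formal testing planned, the consequence is for interpretation, not for type I error or power. It is a cheap improvement to the display of a secondary objective, not an error in a stated figure.

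**What to change.** Keep the observed-case by-visit tables as primary, and add to SAP 4.4:

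- A sentence saying where ET clinical-activity values are shown.
- A flagged sensitivity table of mNIS+7 change that includes each ET value at the next scheduled 6-month time point, with the actual study day shown; and/or a summary of change to the last on-study value including ET, on the pattern of Protocol 9.2.3.
- At each visit, the number assessed out of the number enrolled.

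The cost is SAP wording and about one table, using data already collected. The downside should be footnoted: ET values are single rather than averaged duplicate assessments, and they can fall about 3 months before the nominal month, so they may understate later worsening. That is why they belong in a sensitivity display and not in the primary means. A repeated-measures model is not needed in a descriptive study for which SAP 3.5 plans no covariate adjustment.
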